7.11.1.7 Displays of Pretreatment Events

Analysis Set:All Subjects Who Signed the Informed Consent FormAnalysis Variables:PTEAnalytical Methods:The following summaries will be provided using frequency distribution.PTEs will be coded using the MedDRA and will be summarized using SOC and PT. SOC will

be sorted alphabetically and PT will be sorted in decreasing frequency.

 Pretreatment Events by System Organ Class and Preferred Term
 Serious Pretreatment Events by System Organ Class and Preferred Term The frequency distribution will be provided according to the rules below.
 Number of subjects
 A subject with multiple occurrences of PTE within a SOC will be counted only once in that SOC. A subject with multiple occurrences of PTE within a PT will be counted only once in that that PT.

7.11.2 Clinical Laboratory Evaluations

Hematology and Serum Chemistry

Analysis Set:	Safety Analysis Set					
Analysis Variables :	Hematology					
	RBCs (×10 ¹⁰ /L)	WBCs (×10 ⁸ /L)	Hemoglobin (g/dL)			
	Hematocrit (%)	Platelets (×10 ¹⁰ /L)				
	White blood cell differentiat $(\times 10^8/L)$,	Il (Neutrophils (×10 ⁸ /L), Eosinophils (×10 ⁸ /L), Basophils				
	Monocytes (×10 ⁸ /L), Lympl	hocytes ($\times 10^8/L$))				
	MCH (pg)	MCHC (%)	MCV (fL)			
	Serum Chemistry					
	ALT (U/L)	Alkaline Phosphatase (U/L)	AST (U/L)			
	GGT (IU/L)	Bilirubin (Total) (mg/dL)				
	Lactose Dehydrogenase (U/L)	C-reactive Protein (mg/dL)	Albumin (g/dL)			
	Protein (Total) (g/dL)	Creatinine (mg/dL)	Blood Urea Nitrogen(mg/dL)			
	Uric Acid (mg/dL)	Total Cholesterol (mg/dL)	Phosphorus (mg/dL)			
	Triglycerides (mg/dL)	Glucose (mg/dL)	Potassium (mEq/L)			
	Sodium (mEq/L)	Magnesium (mg/dL)	Calcium (mg/dL)			
	Chloride (mmol/L)					
Visit:	Baseline, Days 2, 5, 8 and 14					
Analytical Methods:	: The following summaries will be provided by dose.					
	 (1) Summary of Laboratory Test Results and Change from Baseline by Visit Descriptive statistics for observed values and changes from baseline (each post-baseline visit - baseline) will be provided for each visit. (2) Case Plots 					

Spaghetti plots will be prepared for each ECG parameters by dose levels.

(3) Summary of Shifts of Laboratory Test Results

Shift tables showing the number of subjects in each category at baseline and each postbaseline visit will be provided. For each laboratory test, the laboratory values will be classified as "Low", "Normal", or "High" relative to the normal reference range provided by the central laboratory. The shift tables will be based on these classifications.

(4) Number and Percentage of Subjects with Markedly Abnormal Values of Laboratory Test results

Overall frequency distributions of MAV after first dose will be provided. If a laboratory test result has both lower and upper MAV criteria, analysis will be performed for each. Further details are given in Appendix.

Urinalysis

Analysis Set:	Safety Analysis Set				
Analysis Variables :	рН	[Min<= - <5.0, 5.0<= - <=8.5, 8.5< - <=Max]			
	Specific gravity	[Min<= - <1.005, 1.005<= - <=1.030, 1.030< - <=Max]			
	Protein	[-, -+, 1+, 2+, 3+, 4+]			
	Glucose	[-, 1+, 2+, 3+, 4+]			
	Nitrites	[-, 1+, 2+]			
	Ketones	[-, 1+, 2+, 3+]			
	Urobilinogen	[-, -+, 1+, 2+, 3+, 4+]]			
	Blood	[-, 1+, 2+, 3+]			
	Urine microscopy				
	RBC/high-power field	[1-5/WF, 6-10/WF, 0-1/LF, 1-5/HF, 6-10/HF, 11-			
		20/HF, 21-50/HF, 51-99/HF, 100≦/HF]			
	WBC/high-power field	[1-5/WF, 6-10/WF, 0-1/LF, 1-5/HF, 6-10/HF, 11-			
		20/HF, 21-50/HF, 51-99/HF, 100≦/HF]			
	Squamous epithelial cells	[1-5/WF, 6-10/WF, 0-1/LF, 1-5/HF, 6-10/HF, 11-			
		20/HF, 21-50/HF, 51-99/HF, 100≦/HF]			
Visit:	Baseline, Days 2, 5, 8, and 14.				
	TTI (11) : :111				

Analytical Methods: The following summaries will be provided by dose. For only specific gravity, summarie (2) will be provided

(1) Summary of Shifts of Urine Laboratory Test Results

Shift tables showing the number of subjects in each category at baseline and each postbaseline visit will be provided.

(2) Case Plots

Plots over time for each subject will be presented.

7.11.3 Vital Signs

Analysis Set:	Safety Analysis Set				
Analysis Variables:	Body Temperature (°C)				
	Systolic Blood Pressure (mmHg)				
	Diastolic Blood Pressure (mmHg)				
	Respiratory Rate (bpm)				
	Pulse (bpm)				
Visit:	Day 1: Predose, 1, 2, 4, 6, and 24 hours post single dose.				
	Days 3-6: Before morning dose.				
	Day 7: Predose, 1, 2, 4, 6, and 24 hours post morning dose				
	Day 14				
Analytical Methods:	For each variable, following summary will be provided by dose.				
	(1) Summary of Vital Signs Parameters and Change from Baseline by Visit				
	Descriptive statistics for observed values and changes from baseline (each post- Day 1:				
	Predose) will be provided for each visit				
	(2) Case Plots				
	Plots over time for each subject will be presented.				
	(3) Number and Percentage of Subjects with Markedly Abnormal Values of Vital Signs				
	Parameters				
	Overall frequency distributions of MAV after first dose will be provided. If a vital sign				
	parameter has both lower and upper MAV criteria, analysis will be performed for each.				
	Further details are given in Appendix.				

7.11.4 12-Lead ECGs

Analysis Set:	Safety Analysis Set				
Analysis Variables:	Heart Rate (bpm)				
	RR Interval (msec)				
	PR Interval (msec)				
	QT Interval (msec)				
	QTcF Interval (msec)				
	QRS Interval (msec)				
	12-Lead ECG Interpretation	["Within Normal Limits",			
		"Abnormal, Not Clinically Significant",			
		"Abnormal, Clinically Significant"]			
Visit:	Day 1: Predose, 1, 2, 4, 6, and 24 hours post single dose.				
	Day 5: Predose, 1, and 2 hours post morning dose.				
	Day 7: Predose, 1, 2, 4, 6, and	24 hours post morning dose			
Analytical Methods:	For each variable other than 12-lead ECG interpretations, summary (1), (2), and (3) will be				
	provided by dose.				
	For 12-lead ECG interpretations, summary (4) will be provided by dose.				
	(1) Summary of ECG Parameters and Change from Baseline by Visit				
	CO	NFIDENTIAL			

Descriptive statistics for observed values and changes from baseline (each post- Day 1: Predose) will be provided for each visit.

(2) Case Plots

Plots over time for each subject will be presented.

(3) Number and Percentage of Subjects with Markedly Abnormal Values of ECG Parameters

Overall frequency distributions of MAV after first dose will be provided. If an ECG parameter has both lower and upper MAV criteria, analysis will be performed for each. Further details are given in Appendix.

(4) Summary of Shifts of ECG Parameters

Shift tables showing the number of subjects in each category at Day 1 Predose and each post-Day 1 Predose visit will be provided.

7.11.5 Other Observations Related to Safety

Not applicable

7.12 Interim Analysis

Not applicable

7.13 Changes in the Statistical Analysis Plan

From the SAP version 1.0, the following parts were updated. In 7.11.2, the units for white blood cell differential modified. In Appendix 1, since there is no abnormal criteria for white blood cell differential in the site, the MAV criteria for white blood cell differential was deleted.

8.0 **REFERENCES**

Not applicable

Appendix 1. Criteria for Markedly Abnormal Values

Hematology, Serum Chemistry, Urinalysis, Vital Signs, and 12-lead ECG (except Upper

MAV Criteria of QTcF Interval)

For each parameter, all evaluable data obtained up to Day 14(or Day 8 for 12-lead ECG) will be classified as a MAV or not. The criteria in the table below will be used. The lower limit of the normal range and the upper limit of the normal range are abbreviated as LLN and ULN.

For each parameter and subject, classifications will be made according to the conditions i) to iii) provided below. The lower and the upper criteria will be considered separately.

- i) A subject with at least one evaluable data after baseline or "Day 1: Predose" that meets the MAV criteria will be classified as a subject with MAV.
- ii) A subject who does not meet condition i) and has at least one evaluable data after baseline or "Day 1: Predose" that doesn't meet the MAV criteria will be considered as a subject without MAV.
- iii) A subject who does not meet conditions i) or ii) will be excluded from the analysis of MAV for that parameter.

Hematology

	Gender	Age	MAV Criteria	
Parameter			Lower Criteria	Upper Criteria
RBCs (×10 ⁶ / μ L)	-	-	<0.8×LLN	>1.2×ULN
Platelets (× $10^3/\mu$ L)	-	-	<75	>600
WBCs (×10 ³ / μ L)	-	-	<0.5×LLN	>1.5×ULN

Serum Chemistry

D. (Gender	Age	MAV Criteria	
Parameter			Lower Criteria	Upper Criteria
Protein (total) (g/dL)	-	-	<0.8×LLN	>1.2×ULN
Albumin (g/dL)	-	-	<2.5	-
Blood urea nitrogen (mg/dL)	-	-	-	>30
Uric acid (mg/dL)	-	-	-	>13.0
Creatinine (mg/dL)	-	-	-	>2.0

	Gender	Age	MAV Criteria	
Parameter			Lower Criteria	Upper Criteria
Total cholesterol (mg/dL)	-	-	-	>300
Triglycerides (mg/dL)	-	-	-	>2.5×ULN
Bilirubin (total) (mg/dL)	-	-	-	>2.0
Sodium (mEq/L)	-	-	<130	>150
Potassium (mEq/L)	-	-	<3.0	>6.0
Chloride (mEq/L)	-	-	<75	>126
Calcium (mg/dL)	-	-	<7.0	>11.5
Phosphorus (mg/dL)	-	-	<1.6	>6.2
Alkaline phosphatase (IU/L)	-	-	-	>3×ULN
AST (IU/L)	-	-	-	>3×ULN
ALT (IU/L)	-	-	-	>3×ULN
GGT (IU/L)	-	-	-	>3×ULN
Glucose (mg/dL)	-	-	<50	>350
Magnesium (mg/dL)	-	_	<1.2	>3.0

Vital Signs

D. (Gender	Age	MAV Criteria	
Parameter			Lower Criteria	Upper Criteria
Systolic blood pressure (mmHg)	-	-	<85	>180
Diastolic blood pressure (mmHg)	-	-	<50	>110
Pulse (bpm)	-	-	<50	>120
Body temperature (°C)	-	-	<35.6	>37.7

12-lead ECG

D. (Gender	Age	MAV Criteria	
Parameter			Lower Criteria	Upper Criteria
Heart rate (bpm)	-	-	<50	>120
QTinterval (msec)	-	-	<=50	>=460
QTcF interval (msec)	_	_	<=50	_

12-lead ECG (Upper MAV Criteria of QTcF Interval)

All evaluable data (ie, non-missing data) obtained up to Day 8 will be classified as a MAV or not. The criteria in the table below will be used. Note that the observed value and the change from Day 1 Predose used for classification should be measurements taken on the same day.

For each subject, classifications will be made according to the conditions i) to iii) provided below.

- i) A subject with at least one evaluable data after Day 1 Predose that meets the MAV criteria will be classified as a subject with MAV.
- ii) A subject who does not meet condition i) and has at least one evaluable data after Day 1 Predose that meets any of the following will be considered as a subject without MAV.
 - Observed value is less than 450 msec and not missing.
 - Change from Day 1 Predose is less than 30 msec and not missing, and observed value is less than 500 msec and not missing.
- iii) A subject who does not meet conditions i) or ii) will be excluded from the analysis of MAV.

Parameter	Gender	Age	MAV Criteria	
			Upper Criteria	
QTcF Interval (msec)	-	-	If either of the following conditions is met:	
			 observed value >=500 change from Day 1 Predose >= 30 and observed value >=450

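### The markedly abnormal value tables for vital signs and numeric ECG parameters cannot separate an abnormality present before dosing from a new one

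*SAP*

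**What the plan says.** **Classification rule (SAP Appendix 1).** Condition i) opens "A subject with at least one evaluable data after baseline" and makes the subject a MAV case if any such value meets the limit. Condition ii), which defines a subject without MAV, also looks only at later values: "A subject who does not meet condition i) and has at least one evaluable data after baseline". Condition iii) then removes subjects who fit neither: "A subject who does not meet conditions i) or ii) will be excluded from the analysis of MAV for that parameter". A subject abnormal before dosing therefore stays in both numerator and denominator.

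**Limits.** The vital sign and ECG limits are absolute. The rows for pulse and ECG heart rate read "Pulse (bpm) - - <50 >120" and "Heart rate (bpm) - - <50 >120". The upper QTcF criterion has its own rule with two arms. One is an observed value of at least 500 msec. The other is a rise of at least 30 msec from Day 1 predose together with a value of at least 450 msec.

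**Planned outputs.** For vital signs, SAP 7.11.3 lists descriptive statistics with change from baseline, case plots, and "3) Number and Percentage of Subjects with Markedly Abnormal Values of Vital Signs" Parameters. On timing it says: "Overall frequency distributions of MAV after first dose will be provided". SAP 7.11.4 gives numeric ECG variables the same three outputs and reserves the shift table for the overall ECG interpretation. Laboratory tests do get shift tables (SAP 7.11.2).

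**Eligibility.** Protocol 7.1 and 7.2 set no numeric limit on pulse or heart rate. Exclusion criterion 23 removes only a clinically significant abnormal ECG, and criterion 24 only a QTcF above 450 msec.

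**The concern.** For pulse, blood pressure, temperature, heart rate and the ECG intervals, the MAV table is the only planned categorical summary. Vital signs and ECG are part of the primary safety endpoint. A reader who sees one low-pulse case in a dose group will want to know whether it appeared on treatment. The table cannot say, because a man with a pulse of 48 before dosing and 48 at every later reading is counted exactly like a man who fell from 65 to 48. With six subjects per active dose, one such case is a visible percentage.

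**Working it through.** The plan states no figure on this point, so there is none to reproduce. The check has four parts.

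**1. Does the rule use the predose value?** Take a subject with pulse 48 at Day 1 predose and at every later reading. Condition i) needs one post-dose value below 50, so it is met and he is a MAV case. Conditions ii) and iii) do not apply. The predose value is never consulted.

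**2. Can such a subject enter?** No criterion sets a lower limit on pulse or heart rate. The QT limit shows the same gap from the documents' own figures. SAP 7.1.1 defines QTcF = QT / (RR/1000)^0.33. For QTcF 430 msec and heart rate 48:

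- RR = 60,000 / 48 = 1,250 msec
- QT = 430 × 1.25^0.33 = 463 msec

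He passes the QTcF limit of 450. Unless the investigator judges his ECG clinically significant, he enters already meeting both the heart rate limit (<50) and the QT limit (≥460).

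**3. Size in one group.** Each cohort has 6 active subjects (SAP 4.4.1), so one subject is 1/6 = 16.7%. The documents give no proportion starting below 50; I assume 5% to 10%. The chance that a group of 6 has at least one is 1 − (1 − p)^6:

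- p = 0.05: 1 − 0.95^6 = 0.265
- p = 0.10: 1 − 0.90^6 = 0.469

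**4. How much would a predose comparison remove?** Post-dose vital sign readings number 5 (Days 1-2) + 4 (Days 3-6) + 6 (Days 7-8) + 1 (Day 14) = 16. Post-dose ECGs number 5 + 3 + 6 = 14. Pulse was simulated with no drug effect, one predose reading and 16 post-dose readings. All of the following inputs are assumptions: population mean 58 to 66 bpm, between-subject SD 6 to 8, within-subject SD 3 to 5.

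| Quantity | Range over the assumed inputs |
|---|---|
| Expected low-pulse MAV subjects per group of 6, current rule | 0.3 to 3.3 |
| Same, counting only subjects not below 50 at predose | 0.2 to 2.4 |
| Share of flagged subjects already below 50 at predose | 12% to 46% |

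The remaining 54% to 88% of flags also arise without any drug effect, because one predose reading is set against many later ones.

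**The case against.** The strongest reply is that this is a choice of table format.

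- **Baseline is visible elsewhere.** SAP 7.11.3 and 7.11.4 plan change-from-baseline summaries and a plot for each subject. Protocol 11.1.5.3 and 11.1.5.4 promise listings of all vital sign and ECG data. With 24 subjects, a reader can trace each flagged case by hand. This stands and limits the harm. It does not repair the MAV table, and group mean changes do not show which flagged subjects began abnormal.
- **The output is not mislabelled.** It claims to count MAVs after first dose, and it does. This stands.
- **The fix is partial.** Part 4 above confirms this.

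Four stronger readings are tempting, and the documents do not support them.

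- **Bias for or against the drug.** Treatment is randomized, with 2 placebo subjects per cohort, and a placebo subject is as likely to start below 50 as an active one. An imbalance would be chance: it can suggest an effect or mask one.
- **Baseline ignored throughout the MAV analysis.** One arm of the upper QTcF criterion uses change from Day 1 predose. Laboratory MAV counts do lack a baseline condition, but the laboratory shift tables partly offset that.
- **A conflict between SAP and protocol.** The protocol promises ECG shift tables only for categorical variables and none for vital signs. The SAP matches it.
- **An effect on dose escalation or stopping.** Entry to Cohort 2 rests on blinded review of safety results (Protocol 6.2). The suspension criteria in Protocol 6.5.4.1 do not use MAV counts.

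**Conclusion.** The point holds as a limited weakness in a descriptive safety table. Apart from the change-based arm of the upper QTcF criterion, MAV status for vital signs and numeric ECG parameters depends on post-dose values alone, and no planned shift table supplies the missing predose category. The absence of a baseline condition and the 17 points per subject follow directly from the documents. The 27% to 47% chance of at least one such subject in a group of 6 rests on the assumed 5% to 10% prevalence, and the simulated ranges on the assumed pulse distribution. Severity is low: the change would be worth having, but the trial's conclusions do not depend on it.

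**What to change.** In SAP 7.11.3, 7.11.4 and Appendix 1, keep the current count and add, by dose:

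- (a) the number of subjects meeting the criterion at Day 1 predose;
- (b) the number meeting it after dosing but not at Day 1 predose.

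State how a subject with no Day 1 predose value is handled in these rows.

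If the rows are extended to laboratory MAVs, use the SAP 7.1.1 baseline (last evaluable value before first dose). The schedule in Protocol 3.0 has no laboratory sample at Day 1 predose; the last one planned before dosing is at Check-in on Day -1.

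The data are already collected, so the cost is a slightly longer table and its programming. Two limits should be noted beside it. Row (b) does not show worsening in a subject already abnormal at predose, which remains visible only in plots and listings. And comparing one predose reading with up to 16 later ones removes only part of the flags unrelated to drug, so row (b) should not be read as a count of drug effects.

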# 6.5.4 Criteria for Premature Termination or Suspension of the Trial

# 6.5.4.1 Criteria for Premature Termination or Suspension of the Trial

The study will be completed as planned unless 1 or more of the following criteria are satisfied that require temporary suspension or early termination of the study.

- 1. New information or other evaluation regarding the safety or efficacy of the study medication that indicates a change in the known risk/benefit profile for TAK-906, such that the risk is no longer acceptable for subjects participating in the study.
- 2. Significant violation of Good Clinical Practice (GCP) that compromises the ability to achieve the primary study objectives or compromises subject safety.
- 3. Two or more subjects in any single cohort or across more than 1 cohort experience any of the Takeda Medically Significant List events (as outlined in Table 10.a).
- 4. Two or more subjects in any single cohort experience a QTcF of >500 msec or an increased QTcF of >60 msec relative to baseline.
- 5. Abnormal liver function:

TAK-906	
Study ID TAK-906-1004	Page 24 of 71
Protocol	6 June 2017

- a. Two or more subjects in any single cohort or across more than 1 cohort experience alanine aminotransferase (ALT) and/or aspartate aminotransferase (AST) elevations of  $>5 \times$  upper limit of normal (ULN) in the absence of a concomitant bilirubin increase.
- b. One or more subjects in any single cohort experience ALT and/or AST elevations of >3 ×ULN in the presence of a total bilirubin increase of >2 ×ULN or an international normalized ratio (INR) of >1.5 without findings of cholestasis or other alternate etiology to explain the elevations (ie, "Hy's Law cases").
- c. Two or more subjects in any single cohort or across more than 1 cohort experience ALT and/or AST elevations of  $>3 \times ULN$  with the appearance of fatigue, nausea, vomiting, right upper quadrant pain or tenderness, fever, rash and/or eosinophilia (>5%).

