# 7.6 Criteria for Discontinuation or Withdrawal of a Subject

Primary reasons for discontinuation or withdrawal of a subject from the study or study drug should be recorded in the eCRF using the following categories. For subject failure, refer to Section 7.5.

1. Death. The subject died on study.

Note: If the subject dies on study, the event will be considered as SAE. See Section 10.2.9.3 for the reporting procedures.

2. AE. The subject has experienced an AE that requires early termination because continued participation imposes an unacceptable risk to the subject's health or the subject is unwilling to continue because of the AE.

In multidose studies, study drug should be discontinued immediately with appropriate clinical follow-up (including repeat laboratory tests, until the subject's laboratory profile has returned to normal/baseline status, see Section 9.2.8), if the following circumstances occur at any time during study drug treatment:

- Liver Function Test (LFT) Abnormalities
  - ALT or AST >8×ULN, or
  - ALT or AST >5×ULN and persists for more than 2 weeks, or

- ALT or AST >3×ULN in conjunction with elevated total bilirubin >2×ULN or INR >1.5, or
- ALT or AST >3×ULN with appearance of fatigue, nausea, vomiting, right upper quadrant pain or tenderness, fever, rash and/or eosinophilia (>5%).
- QT prolongation
  - QTcF >500 msec or  $\Delta$ QTcF (change from baseline in QTcF) >60 msec.
- 3. Protocol deviation. The discovery post-dose that the subject failed to meet protocol entry criteria or did not adhere to protocol requirements, and continued participation poses an unacceptable risk to the subject's health.
- 4. Lost to follow-up. The subject did not return to the clinic and attempts to contact the subject were unsuccessful. Attempts to contact the subject must be documented in the subject's source documentation.
- 5. Withdrawal by subject. The subject wishes to withdraw from the study. The reason for withdrawal, if provided, should be recorded in the eCRF.

Note: All attempts should be made to determine the underlying reason for the withdrawal and, where possible, the primary underlying reason should be recorded (ie, withdrawal due to an AE should not be recorded in the "voluntary withdrawal" category).

- 6. Study terminated by the Sponsor. The Sponsor terminates the study.
- 7. Other

Note: The specific reasons should be recorded in the "specify" field of the eCRF.

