## 11.1.5.4 Other Safety Parameters

ECG parameters are summarized as follows: for continuous variables, the observed values and their changes from baseline will be summarized by dose over each scheduled sampling time using descriptive statistics. For categorical variables, shift tables showing the number of subjects in each category at baseline and each post-baseline visit will be provided by dose. All ECG data will be provided in the data listings.

Physical examination findings will be presented in the data listings.

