7.0 METHODS OF ANALYSIS AND PRESENTATION

7.1 General Principles

7.1.1 Study Definitions

The following definitions and calculation formulas will be used.

- TEAE: An AE whose date of onset occurs on or after the start of study drug. A TEAE whose relationship to study drug is missing will be considered drug-related. A TEAE whose intensity is missing will be considered severe.
- PTE: An AE whose date of onset occurs before the start of study drug..
- Descriptive statistics: number of subjects with non-missing values, mean, standard deviation, maximum, minimum, and quartiles, including geo-mean, geo-CV as needed
- QTcF interval (msec): QT interval (msec) / (RR interval (msec)/1000)^{0.33} (rounded to the nearest whole number)
- Baseline values: The last evaluable observation (ie, non-missing) before the first dose of study drug. If no evaluable observation is obtained before the first dose, the baseline value will be missing.
- TEAE occurred in single dose period: A TEAE occurred prior to start of multiple dosing.
- TEAE occurred in multiple dose period: A TEAE occurred from Day 3 postdose through Day 14 (follow-up visit).

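### The SAP's upper QTcF criterion has no limb on change alone, so a rise above 60 msec from a baseline of 388 msec or less can be counted as not markedly abnormal

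*SAP*

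**What the plan says.** **SAP, Appendix 1, upper QTcF criteria.** A subject is flagged if either of two conditions is met at any evaluable time after Day 1 predose: an observed value of 500 msec or more, or "change from Day 1 Predose >= 30 and observed value >=450". A subject who is not flagged is classed as without an abnormality if at least one value satisfies one of two further conditions. The first is "Observed value is less than 450 msec and not missing", with no limit on change.

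**Protocol, Section 7.6.** The QT criterion for discontinuing a subject is QTcF above 500 msec or, as an alternative, "change from baseline in QTcF) >60 msec".

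**Protocol, Section 6.5.4.1, item 4.** The trial-level criterion uses the same pair of alternatives: "Two or more subjects in any single cohort experience a QTcF of >500 msec or an increased QTcF of >60 msec relative to baseline".

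**SAP, Section 7.11.4.** The numeric ECG parameters get descriptive statistics, individual plots and the abnormality count. The shift table covers only the overall reading: "For 12-lead ECG interpretations, summary (4) will be provided by dose".

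**SAP, Section 7.1.1.** QTcF is "rounded to the nearest whole number".

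**The concern.** The 12-lead ECG is part of the primary safety endpoint, and QTc prolongation is one of three event groups that Protocol Section 6.3.3.1 singles out for closer monitoring. A reader who wants the number of subjects at each dose with a notable QTcF finding will go to the abnormality table. It is the only planned output that classifies subjects by QTcF.

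That table can count as a non-case a subject who meets the protocol's own QT criterion. The subject is not set aside as unevaluable but enters the denominator as negative. The ordering is also odd: 420 to 450 msec (rise 30) is flagged, while 375 to 449 msec (rise 74) is not. With six active subjects per dose, one such subject is the difference between 1/6 and 0/6.

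**Working it through.** The plan gives no figure to reproduce, so the check sets the two rules side by side.

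**Rules.** Let B be Day 1 predose QTcF and X a later value, both in whole msec.
- SAP flag: X ≥ 500, or (X − B ≥ 30 and X ≥ 450).
- SAP non-case: not flagged, and some X < 450, or some X with X − B < 30 and X < 500.
- Protocol criterion: X > 500, or X − B > 60.

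**Change needed for a flag.** When the second SAP limb decides, the change must be at least max(30, 450 − B): 75 msec at B = 375, 50 at B = 400, and 30 at B = 420 or above.

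**Where the rules diverge.** Meeting the protocol criterion through change alone needs X ≥ B + 61. Escaping both SAP limbs then needs X ≤ 449. Both hold only if B + 61 ≤ 449, so B ≤ 388. Missed rises run from 61 to 449 − B:

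| Baseline (msec) | Missed rises (msec) | Values reached (msec) |
|---|---|---|
| 360 | 61–89 | 421–449 |
| 370 | 61–79 | 431–449 |
| 375 | 61–74 | 436–449 |
| 380 | 61–69 | 441–449 |
| 385 | 61–64 | 446–449 |
| 388 | 61 only | 449 |
| 389 and above | none | – |

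For B ≤ 388, any value of 450 or more is a rise of at least 62 and is flagged. The gap is therefore confined to subjects whose values all stay below 450.

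**Enumeration.** Over all whole-msec pairs with B from 300 to 450 and X from B − 50 to 560, 4005 pairs meet the protocol criterion without an SAP flag. All have B ≤ 388 and X ≤ 449, and all satisfy the SAP's non-case condition. As a cross-check, each B contributes 389 − B pairs, and the sum over B = 300 to 388 is 89 × 90 / 2 = 4005. Adding a limb for change above 60 reduces the count to 0.

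**Eligibility.** Exclusion criterion 24 caps QTcF at 450 msec and sets no lower bound, so baselines of 388 or less can enter.

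**Size, under assumptions.** The documents give no QTcF mean, SD or distribution of rises. Assume normal baselines. The share exposed is P(B ≤ 388) = Φ((388.5 − mean)/SD); for example, Φ((388.5 − 400)/20) = Φ(−0.575) = 0.283.

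Exposure is not the miss rate. For that, assume rise = 60 + k, with k geometric from 1 with mean m and independent of baseline, and baselines truncated at 450. A rise is missed when k ≤ 389 − B, so P(miss given B) = 1 − (1 − 1/m)^(389 − B) for B ≤ 388 and 0 otherwise. Averaging over baselines:

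| Mean baseline | Exposed share (SD 15, SD 20) | Missed given rise > 60, m = 10 (SD 15, SD 20) | Missed given rise > 60, m = 20 (SD 15, SD 20) |
|---|---|---|---|
| 390 | 46%, 47% | 28%, 32% | 19%, 23% |
| 400 | 22%, 28% | 12%, 18% | 8%, 12% |
| 410 | 8%, 14% | 4%, 8% | 2%, 5% |

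**The case against.** **A reporting screen need not mirror a stopping rule.** No text says the abnormality table implements the protocol's QT criterion, and thresholds differ elsewhere: ALT and AST are flagged above 3 × ULN, while Section 7.6 uses several other combinations. It is true that the documents do not formally contradict each other. But every transaminase criterion in Section 7.6 requires a value above 3 × ULN, so that screen catches every such case. The QTcF screen does not, and the SAP gives no reason.

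**The rise is visible elsewhere.** This also stands. SAP Section 7.11.4 provides: "Descriptive statistics for observed values and changes from baseline (each post- Day 1: Predose) will be provided for each visit". The SAP's descriptive statistics include the maximum, so with six active subjects per dose a change of 61 or more would show. There are also individual plots, and the protocol says "All ECG data will be provided in the data listings". None of these counts subjects by dose.

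**The discontinuation route would catch it.** Partly. A subject stopped under Section 7.6 would appear in disposition and, if the change is recorded as an adverse event, in the tables of events leading to discontinuation. But the last dose is on the morning of Day 7, and ECGs follow at 1, 2, 4, 6 and 24 hours. A rise first seen there cannot lead to discontinuation. The QTc-associated events listed in Protocol Section 10.2.9.4 are clinical events, so a rise without symptoms need not appear among them.

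**The 388 msec boundary and the miss rates are over-precise.** The boundary is exact only if both rules use the SAP's rounded QTcF and the protocol's baseline is Day 1 predose. A site QTcF taken from the trace could move it by about 1 msec, and without rounding the bound is a baseline below 390. The miss rates rest entirely on assumptions. The protocol also describes TAK-906 as a very weak hERG inhibitor, so such rises may be rare or absent.

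**Conclusion.** The concern holds. A subject with a baseline of 388 msec or less, a rise above 60 msec and all values below 450 msec meets the protocol's QT criterion and is counted as a non-case in the only planned table that classifies subjects by QTcF.

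The boundary follows from the text, given whole-msec QTcF and Day 1 predose as baseline. The frequency does not: the conditional miss rate of about 2% to 32% depends on the assumed baselines and rises, and the number of affected subjects may be zero.

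The consequence is limited to that summary. No stopping decision or other planned estimate changes. It should be corrected because it concerns a primary-endpoint safety table and the correction is nearly free.

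**What to change.** Reconcile the SAP table with the criterion already in the protocol:

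1. In SAP Appendix 1, add a change from Day 1 predose above 60 msec as a third alternative in the upper QTcF criteria. These subjects are then flagged and no longer fall into the non-case class.
2. Show that category as its own row, counted independently of the other limbs, for each TAK-906 dose and pooled placebo.
3. If the existing definition must be kept, add the separate row alone, with a footnote that being classed as without a markedly abnormal value does not exclude a change above 60 msec.

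The cost is one line in the SAP and one table row. Data collection and the protocol's stopping rules are unchanged, and no new clinical threshold is introduced.
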